9.7 DATA ANALYSIS

Descriptive analysis will be means, medians, quantiles, proportions (with their respective 95% confidence intervals and SE when relevant) and contingency tables according to the nature of the variables. As a dispersion measurement the standard deviation and the interquartile range will be calculated.

Statistical analysis will be performed using the SAS software.

The statistical analysis will be done on all evaluable patients i.e. patients who enter the study without inclusion-exclusion criteria violations and with at least one TSQM-9 domain score (effectiveness, convenience and global satisfaction) calculated. Enrolled patients not evaluable for analysis will be described in terms of frequency of violations and according main socio-demographic variables (such as age and gender), clinical (such as disease severity and number of exacerbations in the 12-month before enrollment) and treatment satisfaction scores (if available) at baseline.

Patients with missing values will not be excluded from the analysis, their data will not be replaced; frequency of missing data will be given for all analyzed variables. Lost to follow up patients will be analyzed until their last available visit.

Appropriate descriptive statistics for main socio-demographic (gender, age, race, education and employment status, smoking habits) and clinical variables (medical history for COPD and not, disease severity and awareness) at baseline visit will be presented to describe the study population at inclusion. Patients at inclusion in the study will be also described in terms of ongoing pharmacological and non pharmacological treatments for COPD.

Moreover, the study population will be described in terms of number of exacerbations occurred during study period and changes in COPD medication since baseline.

The study objectives will be evaluated as below described.

Primary objective

The patients' satisfaction for medical treatment will be assessed by the 9-item Treatment Satisfaction Questionnaire for Medication (TSQM-9) at each study visit (45, 46). TSQM-9 is a self-rated tool for evaluating patient satisfaction to medical therapy. It is composed by 3 domains covering efficacy, convenience and global treatment satisfaction. TSQM-9 scores will be calculated according to author's instructions and summarized at each time point on all evaluable patients. Patients lost to follow up will be considered until their last available visit.

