- Inclusion criterion "4. Patients requiring regular treatment according to GOLD guidelines, i.e.: undergoing stable pharmacological treatment for COPD since at least 3 months" not checked in the PROTOCOL DEVIATION FORM [\[F24_PROTOCOL_DEVIATION_FORM.PD_CI_4\]](#) AND
- COPD Pharmacological therapy form: Start date of therapy (dd/mmm/yyyy) not missing AND (Start date of therapy (dd/mmm/yyyy) [\[F20_COPD_PHARMACOLOGICAL_THERAPY.START_DATE_THER\]](#) < Date of enrolment visit (dd/mm/yyyy) - 3*30.4375 [\[_PatientInfo.Date_enrollment\]](#) OR Start date of therapy (dd/mmm/yyyy) > Date of enrolment visit (dd/mm/yyyy)) AND
- COPD Pharmacological therapy form: End date of therapy (dd/mmm/yyyy) [\[F20_COPD_PHARMACOLOGICAL_THERAPY.END_DATE_THER\]](#) = missing OR End date of therapy (dd/mmm/yyyy) > Date of enrolment visit (dd/mm/yyyy) [\[_PatientInfo.Date_enrollment\]](#)

Criterion 5: Written informed consent to both participation in the study and privacy form

- Question "5. Is a written informed consent to both participation in the study and privacy form available?" = "Yes" [\[F01_INC_EXC_CRITERIA.CI_5\]](#) AND
- Inclusion criterion "5. Written informed consent to both participation in the study and privacy form" not checked in the PROTOCOL DEVIATION FORM [\[F24_PROTOCOL_DEVIATION_FORM.PD_CI_5\]](#) AND
- Date of informed consent signature (dd/mm/yyyy) not missing [\[_PatientInfo.Date_CI\]](#) AND
- Date of privacy form signature (dd/mm/yyyy) not missing [\[_PatientInfo.Date_privacy\]](#) AND
- Date of informed consent signature (dd/mm/yyyy) = Date of privacy form signature (dd/mm/yyyy) AND
- Date of informed consent signature (dd/mm/yyyy) ≤ Date of enrolment visit (dd/mm/yyyy)

Criterion 6: Patients capable of discernment and able to read or write in Italian language

- Question "6. Is the patient capable of discernment and able to read or write in Italian language?" = "Yes" [\[F01_INC_EXC_CRITERIA.CI_6\]](#) AND
- Inclusion criterion "6. Patients capable of discernment and able to read or write in Italian language" not checked in the PROTOCOL DEVIATION FORM [\[F24_PROTOCOL_DEVIATION_FORM.PD_IC_6\]](#)

Exclusion criteria**Criterion 7: Patients who are currently participating in a clinical trial on experimental drugs**

- Question "7. Does the patient currently participate in a clinical trial on experimental drugs?" = "No" [\[F01_INC_EXC_CRITERIA.EC_1\]](#) AND

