The Morisky medication Adherence Scale 4 items (MMAS-4) is a self-reported, medication-taking behavior scale and consists of four questions about the way patients might experience drug errors or omissions. Each item [F13_MMAS_4.MMAS_4_1 - MMAS_4_4] has a scoring scheme of "Yes" = 0 and "No" = 1. Items are summed to give a non-adherence score ranging from 0 to 4; a higher score means better adherence to therapy (Morisky DE, Green LW, Levine DM. Concurrent and predictive validity of a self-reported measure of medication adherence. *Med Care*. 1986 Jan;24(1):67-74).

The score can be calculated if at least 3 out of 4 of the items are completed. If only one item is omitted, the value for the missing item is the group median of this item that has been completed by all eligible participants. This median value will be imputed for all eligible cases who did not answer this item.

Changes in the MMAS-4 score at each follow-up visit from enrollment will be calculated, for each patient, as the following difference: (score at 6/12 months - score at enrollment), if both scores are available.

COPD pharmacological treatments (classes) ongoing at enrollment

All COPD pharmacological treatments having "End date of therapy" [F20_COPD_PHARMACOLOGICAL_THERAPY.END_DATE_THER] > "Date of enrollment visit" [PatientInfo.Date_enrollment] OR ("End date of therapy" missing and "Ongoing at the end of observation?" [F20_COPD_PHARMACOLOGICAL_THERAPY.ONGOING_THER] = "Yes").

Drug names will be coded by CDM and grouped according to the following categories:

- LAMA alone
- LABA alone

- ICS alone
- LABA + LAMA (Fixed dose combination or not)
- LABA + ICS (Fixed dose combination or not)
- LABA + LAMA + ICS
- SABA or SAMA on demand
- Other: pharmacological therapies for COPD not included in the previous classes.

Categories above are not mutually exclusive: a patient could be classified in more than one category (i.e. if a patient is receiving LABA and SABA on demand, [REDACTED] will be classified both in the “LABA alone” and in the “SABA or SAMA on demand” classes). Only therapies for COPD will be considered (i.e. those records with field Therapy for [F20_COPD PHARMACOLOGICAL THERAPY.THERAPY_FOR] = “COPD”), while therapies for COPD exacerbations or for COPD-related adverse events will not be considered nor classified.

COPD pharmacological treatments (classes) ongoing at 6- and 12-month follow-up visit

At each follow-up visit, all COPD treatments classes (see algorithm above) having

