- (“Start date of therapy” [F20_COPD PHARMACOLOGICAL THERAPY.START_DATE_THER] not missing AND < “Date of follow up visit” [F19_PATIENT_DISPOSITION.PD_2]) AND
- “End date of therapy” [F20_COPD PHARMACOLOGICAL THERAPY.END_DATE_THER] not missing AND > “Date of follow up visit” [F19_PATIENT_DISPOSITION.PD_2]) OR (“End date of therapy” missing AND “Ongoing at the end of observation?” [F20_COPD PHARMACOLOGICAL THERAPY.ONGOING_THER] = “Yes”).

Drug names will be coded by CDM and grouped according to the categories specified above.

Only therapies for COPD will be considered (i.e. those records with field Therapy for [F20_COPD PHARMACOLOGICAL THERAPY.THERAPY_FOR] = “COPD”), while therapies for COPD exacerbations or for COPD-related adverse events will not be considered.

COPD pharmacological treatments: fixed and non-fixed therapy

Patients with fixed COPD pharmacological treatments are those having at least one record of the COPD PHARMACOLOGICAL THERAPY form with “Is it a fixed dose combination?” [F20_COPD PHARMACOLOGICAL THERAPY.DOSE_2] = “Yes” for therapies ongoing at enrollment (see above).

Patients with non-fixed COPD pharmacological treatments are those having at least one record of the COPD PHARMACOLOGICAL THERAPY form with “Is it a fixed dose combination?” [F20_COPD PHARMACOLOGICAL THERAPY.DOSE_2] = “No” for therapies ongoing at enrollment (see above).

Patients who satisfy both conditions will be defined as **patients receiving both COPD pharmacological fixed and non-fixed therapy** at enrollment.

Data manager will check the congruence between the field “Drug” [F20_COPD PHARMACOLOGICAL THERAPY.DRUG] and the question “Is it a fixed dose combination?”: if any fixed dose drug will be entered in the field “Drug” and the question “Is it a fixed dose combination?” = “No” a query will be sent to the investigator. The vice-versa will be checked as well.

Only therapies for COPD will be considered, while therapies for COPD exacerbations or for COPD-related adverse events will not be considered.

COPD pharmacological treatments: patients switching and not switching treatments

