- Absolute and relative frequency of Patients with oxygen therapy during the observational period (see 'Computed variables' chapter)

Percentages will be computed out of the total number of patients evaluable for the FAS.

Table 31. List of oxygen therapies

List of the following variables:

- Patient ID
- "Date of enrollment visit" [[_PatientInfo.Date_enrollment](#)]
- "Kind of therapy" [[F21_OXYGEN_THERAPY.KIND_OF_THER](#)]
- "Drug" [[F21_OXYGEN_THERAPY.DRUG](#)]
- "Flow (L/min)" [[F21_OXYGEN_THERAPY.FLOW](#)]
- "Hours per day" [[F21_OXYGEN_THERAPY.HOURS](#)]
- "Start date of therapy" [[F21_OXYGEN_THERAPY.START_DATE_NF](#)]
- "Ongoing" [[F21_OXYGEN_THERAPY.ONGOING_NF_THER](#)]
- "End date of therapy" [[F21_OXYGEN_THERAPY.END_DATE_NF](#)]
- "Therapy for" [[F21_OXYGEN_THERAPY.NF_THER_FOR](#)]

Only patients evaluable for the FAS will be considered.

Table 32. Patients receiving fixed/non-fixed dose therapies for COPD at enrollment

The table will provide:

- distribution of patients with COPD pharmacological fixed dose therapy at enrollment (see 'Computed variables' chapter);
- distribution of patients with COPD pharmacological non-fixed dose therapy at enrollment (see 'Computed variables' chapter);
- distribution of patients receiving both COPD pharmacological fixed and non-fixed therapy at enrollment (see 'Computed variables' chapter).

Percentages will be computed out of the total number of patients evaluable for the FAS.

Table 33. COPD pharmacological treatments ongoing at enrollment

The table will provide:

- distribution of COPD pharmacological treatments (classes) ongoing at enrollment (see 'Computed variables' chapter).

Percentages will be computed out of the total number of patients evaluable for the FAS.

Table 34. COPD pharmacological treatments ongoing at 6-month follow-up visit

The table will provide:

- distribution of COPD pharmacological treatments (classes) ongoing at 6-month follow-up visit (see 'Computed variables' chapter)

Percentages will be computed out of the total number of patients evaluable for the FAS.

Table 35. COPD pharmacological treatments ongoing at 12-month follow-up visit

The table will provide:

- distribution of COPD pharmacological treatments (classes) ongoing at 12-month follow-up visit (see 'Computed variables' chapter)

Percentages will be computed out of the total number of patients evaluable for the FAS.

Table 36. Medications for adverse events

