- **Table 26. Specialist outpatient visits: patients' distribution:** Table output will be verified by another BS or CDM ; moreover, randomly chosen patients (20% of evaluable patients) will be checked by a CDM or another BS in order to assess whether Number of specialist outpatient visits per patient during observation period is correctly computed according to the algorithm described in the SAP
- **Table 27. General practitioner visits: patients' distribution:** Table output will be verified by another BS or CDM ; moreover, randomly chosen patients (20% of evaluable patients) will be checked by a CDM or another BS in order to assess whether Number of general practitioner visits per patient during observation period is correctly computed according to the algorithm described in the SAP
- **Table 28. Laboratory tests: patients' distribution:** Table output will be verified by another BS or CDM ; moreover, randomly chosen patients (20% of evaluable patients) will be checked by a CDM or another BS in order to assess whether Number of laboratory tests/examinations per patient during observation period is correctly computed according to the algorithm described in the SAP
- **Table 30. Oxygen therapy:** Table output will be verified by another BS or CDM ; moreover, randomly chosen patients (10% of evaluable patients) will be checked by a CDM or another BS in order to assess whether Patients with oxygen therapy during the observational period were correctly identified according to the algorithm described in the SAP
- **Table 31. List of oxygen therapies:** 3 patients will be verified with respect to DB content
- **Table 32. Patients receiving fixed/non-fixed dose therapies for COPD ongoing at enrollment:** randomly chosen patients (10% of evaluable patients) will be checked by a CDM or another BS in order to assess whether patients with COPD pharmacological fixed and/or non-fixed dose therapy ongoing at enrollment were correctly identified according to the algorithm described in the SAP
- **Table 33. COPD pharmacological treatments ongoing at enrollment:** randomly chosen patients (10 for each COPD pharmacological treatment category) will be checked by a CDM or another BS in order to assess whether the patient was correctly classified according to the algorithm described in the SAP.
- **Table 37. Correlation between patients' satisfaction and resource utilization (including drugs):** another BS will verify the correlations coefficients and p-values

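### The SAP rule for COPD treatments ongoing at enrolment has no start-date condition, so applied literally it counts drugs started during follow-up as enrolment treatment in Tables 32 and 33

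*SAP*

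**What the plan says.** Protocol section 9.7 sets the aim: "Patients at inclusion in the study will be also described in terms of ongoing pharmacological and non pharmacological treatments for COPD".

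SAP section 3 turns this into a record-level rule on the COPD pharmacological therapy log (form F20). The first branch is "All COPD pharmacological treatments having 'End date of therapy' [F20_COPD_PHARMACOLOGICAL_THERAPY.END_DATE_THER] > 'Date of enrollment visit' [PatientInfo.Date_enrollment". The second takes records with no end date that are marked as ongoing at the end of observation. The only other filter is that the therapy was given for COPD, which concerns indication, not time.

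Two tables rest on this rule:

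- Table 33 (SAP section 4.10) reports the "distribution of COPD pharmacological treatments (classes) ongoing at enrollment" and points back to the computed-variables chapter.
- Table 32 reports fixed and non-fixed therapy, which section 3 defines "for therapies ongoing at enrollment (see above".

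The rule for the 6- and 12-month visits, also in section 3, does contain a start-date test. The start date must be "not missing AND < “Date of follow up visit".

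**The concern.** A drug is ongoing on a given day if it started on or before that day and had not yet ended. The enrolment rule tests only the second half. That would be harmless if the log held nothing but drugs already in use at enrolment, but it does not. Criterion 4 of the Full Analysis Set (SAP section 2.1) expressly accepts F20 records with "OR Start date of therapy (dd/mmm/yyyy) > Date of enrolment visit (dd/mm/yyyy". The switcher definition in section 3 likewise treats drugs started after enrolment as a group of their own within the same log.

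What is at stake is the description of the cohort's COPD medication at inclusion. A patient on a LAMA at enrolment who adds a LABA in month 5 has both records returned by the rule, and can be shown as LABA + LAMA at enrolment instead of LAMA alone. In Table 32, a fixed combination started during follow-up would add to the fixed-dose or both categories.

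**Working it through.** The plan gives no figure to reproduce; the check is one of logic.

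**Inputs.** The enrolment rule, the follow-up rule and the table cross-references come from SAP sections 3 and 4.10. The content of the log comes from SAP section 2.1 (criterion 4) and the switcher definition in section 3.

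**Step 1: the rule as written.** With enrolment date E:

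included = (end recorded AND end > E) OR (end missing AND ongoing = Yes)

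**Step 2: apply it to a drug with start > E.** Such a record has three possible states.

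| State of the record | Returned as ongoing at enrolment? |
|---|---|
| End date recorded | Yes, always: end ≥ start > E, so end > E |
| End date missing, ongoing = Yes | Yes |
| End date missing, ongoing not Yes | No |

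Only the incompletely recorded state escapes.

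**Step 3: enumerate.** Take every start from day 1 to day 365 after enrolment, with every end date from the day after the start up to day 399, or still ongoing. A start on day s gives 400 − s records, so the total is 365 × 400 − (365 × 366)/2 = 146,000 − 66,795 = 79,205.

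- Rule as written: 79,205 of 79,205 returned.
- With start ≤ E added to both branches: 0 of 79,205 returned.

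This counts artificial records. It is not an estimate of patients.

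**Step 4: check that true enrolment drugs survive the added condition.**

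| Record (days from enrolment) | As written | With start ≤ E |
|---|---|---|
| Start −400, still ongoing | Returned | Returned |
| Start −400, stopped day 100 | Returned | Returned |
| Start −400, stopped day −50 | Not returned | Not returned |
| Start day 90, stopped day 200 | Returned | Not returned |
| Start day 250, still ongoing | Returned | Not returned |

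**Step 5: compare with the follow-up rule.** Take a drug started in month 7 and stopped in month 10, with visits at months 6 and 12. It is not in Table 34 (7 is not before 6) and not in Table 35 (10 is not after 12). It is in Table 33, because 10 > 0. A drug taken only between the two follow-up visits would thus appear only in the enrolment table.

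**Step 6: trace the reach.** Tables 32 and 33 use the rule. The switcher and therapy-count variables carry their own definition in section 3, and the therapy counts in the Table 37 correlations use that one. The TSQM-9 summaries and the repeated-measures models do not refer to enrolment drug class at all.

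**The case against.** The strongest reply is that the intent is plain. The variable is named as ongoing at enrolment, the switcher definition keeps later starts apart, and a competent programmer may add the missing test unprompted. That is fair, and it is why the error is conditional on literal application. But section 3 gives field-level algorithms so that such choices are not left to the programmer.

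A second reply is quality control. The specific check for Table 33 is made "in order to assess whether the patient was correctly classified according to the algorithm described in the SAP", and the Table 32 check is framed the same way, so neither would detect a gap in the algorithm itself. A reader might infer that the SAP's controls would simply confirm the wrong class. That goes too far: section 6 also provides a general review of all results for coherence and plausibility, and an independent consistency review of the tables. These might catch the problem, although nothing directs them to it.

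Third, the table layouts in SAP section 5 are not in the text available. A clarifying note there can be neither asserted nor excluded.

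Two further inferences are not supported:

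- **That the follow-up rule is also wrong.** Its AND/OR grouping looks ambiguous because a bracket is missing, but the bracket may have been lost when the text was extracted. The two-bullet layout favours applying the start-date test throughout.
- **That the added condition would drop enrolment drugs with no recorded start date.** Criterion 4 already requires a non-missing start date, and Tables 32 and 33 are restricted to the Full Analysis Set. The risk remains only if criterion 4 is not applied to every COPD record, which the SAP does not state.

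**Conclusion.** The rule is wrong as written, and no passage available for review repairs it. Followed literally, it returns every drug started after enrolment that has either a recorded end date or an ongoing flag of Yes, and so misdescribes treatment at inclusion in Tables 32 and 33.

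How many patients this touches cannot be derived: the documents give no rate of add-on or switching. Not every later start matters. A change within a class leaves Table 33 unchanged. Because the classes are not mutually exclusive, a later on-demand SABA adds a row for the patient and does not move the patient from one row to another.

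A reader might infer that the satisfaction results are affected. They are not. The effect stops at two descriptive tables, and the protocol pools all treatments for its analyses. The conclusion rests on two assumptions: that the programming follows section 3 to the letter, and that the unseen table layouts add no start-date condition.

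**What to change.** In SAP section 3, add to both branches of the enrolment rule the condition that the start date of therapy is on or before the date of the enrolment visit:

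start ≤ E AND [(end recorded AND end > E) OR (end missing AND ongoing = Yes)]

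This complements the test of start after enrolment already used in the switcher definition. Table 32 inherits the correction through its cross-reference.

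State whether FAS criterion 4 applies to every COPD record. If it does, nothing more is needed. If one qualifying record is enough, query or list COPD records with a missing start date, so that drugs truly in use at enrolment are not lost.

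The cost is one added condition and reprogramming of Tables 32 and 33. The FAS denominator stays as planned, and no new data are required.

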9.5 STUDY SIZE

The sample size was determined on the basis of feasibility criteria. In fact, according to the volume of patients managed by the centres involved in this study, inclusion of 400 subjects (20 patients/center) with the characteristics defined at Inclusion/Exclusion criteria paragraphs is deemed reasonable for the planned enrolment period (8 months). Assuming a drop-out rate ranging from of 5% to 20% (including not evaluable,lost-to follow up and not on treatment patients), effective sample size is expected to range between 320 (drop out=20%) and 380 (drop out=5%).

An evaluation of the possible achievable precision of the estimates was performed considering the primary objective of the study. No data on treatment satisfaction is available about COPD patients specifically, therefore available literature data was used as a reference to evaluate possible scenarios. In particular, literature data about TSQM was found on multiple sclerosis, psoriasis, etc, showing the global satisfaction mean score ranging from 54.4 to 79.7 (17,18)].

Table 2 shows the 95% confidence interval half-width and standard error (SE) of the expected mean of global satisfaction score under different sample sizes.

| | | | | |
|------------------------------------|-------------|-------|-------------|-------|
| Expected Mean (SD) | 54.4 (21.4) | | 79.7 (16.6) | |
| Sample Size | 380 | 320 | 380 | 320 |
| 95% confidence interval half width | 2.152 | 2.345 | 1.669 | 1.819 |
| Standard error (SE) | 1.098 | 1.196 | 0.852 | 0.928 |

Table 2. 95% confidence interval (CI) half-width and standard error (SE) of the expected mean assuming N=380/320 evaluable patients [19]

In all considered scenarios the relative error of the estimate (CI half-width/expected mean) is lower than 30%. The lower the sample size and the higher the standard deviation, the lower the estimate precision.

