- Exclusion criterion "1. Patients who are currently participating in a clinical trial on experimental drugs" not checked in the PROTOCOL DEVIATION FORM [\[F24_PROTOCOL_DEVIATION_FORM.PD_EC_1\]](#)

Criterion 8: Patients naïve to pharmacological treatment for COPD

- Question "8. Is the patient naïve to pharmacological treatment for COPD?" = "No" [\[F01_INC_EXC_CRITERIA.EC_2\]](#) AND
- COPD Pharmacological therapy form: Start date of therapy (dd/mm/yyyy) (earliest record) not missing AND
- Exclusion criterion "2. Patients naïve to pharmacological treatment for COPD" not checked in the PROTOCOL DEVIATION FORM [\[F24_PROTOCOL_DEVIATION_FORM.PD_EC_2\]](#)

Criterion 9: Diagnosis of Asthma COPD Overlap Syndrome (ACOS)

- Question "9. Does the patient have a diagnosis of Asthma COPD Overlap Syndrome (ACOS)?" = "No" [\[F01_INC_EXC_CRITERIA.EC_3\]](#) AND
- Exclusion criterion "3. Diagnosis of Asthma COPD Overlap Syndrome (ACOS)" not checked in the PROTOCOL DEVIATION FORM [\[F24_PROTOCOL_DEVIATION_FORM.PD_EC_3\]](#)

Other criteria**Criterion 10: patients with at least one Treatment Satisfaction Questionnaire for Medication (TSQM-9) domain score calculated at enrollment visit**

- TSQM-9 items #1,2,3 [\[TSQM9_1-3\]](#) not missing & ≠ "Non risponde" at enrollment visit, OR
- TSQM-9 items #4,5,6 [\[TSQM9_4-6\]](#) not missing & ≠ "Non risponde" at enrollment visit, OR
- TSQM-9 items #7,8,9 [\[TSQM9_7-9\]](#) not missing & ≠ "Non risponde" at enrollment visit

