4 CONTENTS

The analyses will be performed on the Analysis set specified for each table.

Missing data will not be imputed and so patients with missing data will be excluded from the analyses of that variable(s).

If the investigator is unable to collect the requested information the data will be “NK” (Not Known) or “NA” (Not Available), if the investigator did not record the information the data will be “Not Recorded”.

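### A COPD drug with no end date counts as ongoing at enrolment only if it was still ongoing at the end of observation, although FAS criterion 4 accepts the same record without that condition

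*SAP*

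**What the plan says.** Two rules in the SAP read the same therapy form (F20).

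- **Section 3, treatment classes ongoing at enrolment.** A COPD record counts if its end date is after the enrolment visit. If there is no end date, the rule is "End date of therapy' missing and 'Ongoing at the end of observation" equal to Yes. No start-date condition is given. Table 33 uses this variable. Table 32 inherits it, because fixed and non-fixed therapy are defined "for therapies ongoing at enrollment (see above").
- **Section 2.1, FAS criterion 4.** The end-date condition is "missing OR End date of therapy (dd/mmm/yyyy) > Date of enrolment visit (dd/mm/yyyy"). The end-of-observation answer is not consulted.

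The other FAS rules do not consult it either. Criterion 8 asks for "Start date of therapy (dd/mm/yyyy) (earliest record) not missing AND" two answers about being treatment-naive. The questionnaire rule needs enrolment data only: "Criterion 10: patients with at least one Treatment Satisfaction Questionnaire for Medication (TSQM-9) domain score calculated at enrollment visit".

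For Tables 32 to 35, SAP section 4.10 states: "Percentages will be computed out of the total number of patients evaluable for the FAS". SAP section 4 foresees unknown values: "If the investigator is unable to collect the requested information the data will be" NK or NA. It also says that missing data are not imputed and that the patient is left out for that variable.

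The 6- and 12-month classes (Tables 34 and 35) repeat the same handling of a missing end date, this time with a start-date condition.

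**The concern.** What a patient took at enrolment is a baseline fact. Section 3 makes it depend, for records without an end date, on an answer that describes the end of observation, up to about a year later. The rule that admits patients to the FAS does not. The two can therefore disagree on one record: the patient qualifies as being on stable treatment, and the drug behind that qualification then disappears from the table describing treatment at enrolment.

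At stake is the description of ongoing treatment at inclusion that Protocol 9.7 promises, together with its 6- and 12-month counterparts. Because the FAS is defined by stable COPD treatment, an FAS patient with no treatment class contradicts the population definition.

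**Working it through.** **Inputs.** The two rules above; 400 planned patients and "Assuming a drop-out rate ranging from of 5% to 20"% (Protocol 9.5).

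**1. The plan's own figure.** Effective size = 400 × (1 − d). For d = 5%, 400 × 0.95 = 380. For d = 20%, 400 × 0.80 = 320. Both match Protocol 9.5.

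**2. The two rules side by side.** Take a drug started 200 days before enrolment. That satisfies criterion 4's start-date limit of 3 × 30.4375 = 91.3 days.

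| End date | Ongoing at end of observation | Criterion 4 dates | Counted in Table 33 |
|---|---|---|---|
| Missing | Yes | met | yes |
| Missing | No | met | **no** |
| Missing | blank or NK | met | **no** |
| After enrolment | any | met | yes |
| Before enrolment | any | not met | no |

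For drugs started before enrolment, the rules disagree in one situation only: no end date and an answer other than Yes.

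**3. Does anything else remove the patient?** No. Criteria 8 and 10 need nothing from follow-up, so a patient last seen at enrolment can remain in the FAS. The stated denominator of Tables 32 and 33 is then the whole FAS.

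**4. Effect within a patient.** If every COPD record is of this kind, the patient has no class. If only some are, the class changes. Suppose a LABA and a LAMA are recorded separately and the LAMA record is dropped. The patient moves from LABA + LAMA to LABA alone. With 400 in the FAS, one such patient lowers the combination by 1/400 = 0.25 percentage points and raises the single-drug class by the same amount.

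**5. Would the planned checks find it?** SAP section 6 checks Table 33 on 10 patients per treatment category, so a patient without a category is never sampled. The 10% check of Table 32 tests agreement with the SAP algorithm, so it would confirm the output. The only check on this form that section 3 names concerns the fixed-dose answer.

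**6. Size.** Let f be the assumed share of drop-outs whose COPD records all lack both an end date and a Yes. Affected patients k = 400 × d × f, taking all 400 as the FAS.

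| f (assumed) | d = 5% | d = 20% |
|---|---|---|
| 0 | 0 | 0 |
| 25% | 5 (1.25%) | 20 (5%) |
| 50% | 10 (2.5%) | 40 (10%) |
| 100% | 20 (5%) | 80 (20%) |

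As an illustration, assume a class truly used by 40%, with affected patients having the same treatment mix as the rest and losing all their records. The reported share is 40% × (1 − k/400). That is 39.5% for k = 5 and 32% for k = 80. The last column and bottom row are ceilings, because the protocol's drop-out also covers patients who are not evaluable or not on treatment.

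**7. An error in the other direction.** Because section 3 sets no start-date condition, a drug started 30 days after enrolment and still ongoing counts as ongoing at enrolment. This can hide part of the loss.

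**The case against.** The strongest reply is that the problem cell may be empty. No document says how the end-of-observation answer is completed for a patient who is lost. The SAP refers to an end-of-observation visit besides the 6- and 12-month visits, and Protocol 9.7 analyses lost patients up to their last available visit. A site could enter Yes as of last contact, and nothing would be dropped. A record with neither an end date nor an ongoing answer is incomplete, and SAP section 6 describes on-line and off-line checks, with lock only after data quality is approved. The eCRF and the Data Validation Plan, which would settle this, are not available here. All of this stands, and it is why the range starts at zero. It does not remove the conflict: section 6 itself allows for missing or inconsistent data remaining after cleaning, and the written rule is wrong for such a record.

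A second reply is that the table layouts are not shown and may contain an unknown row, and that section 4 excludes patients with missing data. That is possible, but the FAS denominator in section 4.10 points the other way, and its table text mentions no such row.

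Two stronger readings are tempting. A reader might infer that patients lost to follow-up will appear untreated, so that enrolment treatment is biased towards completers. The documents do not support this, since they do not link the answer to loss to follow-up. A reader might also infer that each affected patient lowers every class percentage. That is false: a patient affects only the classes concerned, and losing one record of a combination can raise a single-drug class.

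**Conclusion.** The point holds as an inconsistency between FAS criterion 4 and the section 3 rule. On a record that started before enrolment, has no end date and is not answered Yes, the SAP admits the patient but leaves the drug out of Tables 32 and 33. The same missing-end-date handling carries into Tables 34 and 35.

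The number affected is unknown. It is zero if sites always enter Yes as of last contact or if cleaning resolves every record. The 20 to 80 patients implied by the planned drop-out are a loose ceiling that should not be expected in practice. The shares f and the 40% class are assumptions for illustration. The consequence is limited to descriptive treatment tables. The primary TSQM-9 summaries do not use this variable, and the protocol pools all treatments throughout. The change is worth making because the rule is wrong when followed as written, the stated checks would not reveal it, and the correction is cheap.

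**What to change.** In SAP section 3, define a COPD record as ongoing at enrolment when the start date is on or before the enrolment date AND either the end date is after enrolment, or the end date is missing and the end-of-observation answer is Yes, blank or NK.

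Records answered No with no end date should not simply be counted, since the drug may have stopped before enrolment. Query them or show them as unknown, and treat them the same way in criterion 4 and in Tables 32 and 33.

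Apply the same missing-end-date handling to the 6- and 12-month classes, for visits that took place.

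Add a check that every FAS patient has at least one class, or an explicit unknown entry, in Table 33. This would also reveal a patient whose only records started after enrolment, since criterion 4's date test lets such records through.

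With these changes, a drug that started more than three months before enrolment is handled alike by criterion 4 and by Tables 32 and 33, so the two disagreeing rows in the comparison disappear. The cost is a short wording change, one programming condition, one consistency check and any queries on the No records. No new data collection is needed. If cleaning has already resolved every record, the missing-end-date change alters nothing, and the start-date condition only removes drugs begun after enrolment.
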